Rate of Urinary Tract Infection (UTI) Events	Dichotomous 1=yes 0=no	The frequency of acute UTI events will be taken from all adverse event reporting forms submitted for a participant. The outcome variable will be coded with a value of "Yes" if the participant had any reported acute UTIs over their study duration, identified by MEDRA coding preferred term of "Urinary tract infection" and "recurrent" is NOT specified by verbatim adverse event term or comments. If no acute UTI events were reported for a participant, the outcome variable will be coded with a value of "No".Final database lock review took efforts to query sites for participants with questionable urine test results and get PI confirmation that all necessary events had been reported.
Rate of recurrent Urinary Tract Infection (UTI) Events	Dichotomous 1=yes 0=no	The frequency of recurrent UTI events will be taken from all adverse event reporting forms submitted for a participant. The outcome variable will be coded with a value of "Yes" if the participant had any reported recurrent UTIs over their study duration, identified by MEDRA coding preferred term of "Urinary tract infection" and "recurrent" is specified by verbatim adverse event term or comments. If no recurrent UTI events were reported for a participant, the outcome variable will be coded with a value of "No". Final database lock review took efforts to query sites for participants with questionable urine test results and get PI confirmation that all necessary events had been reported.
Rate of Urinary Retention Events	Dichotomous 1=yes 0=no	The frequency of urinary retention events will be taken from all adverse event reporting forms submitted for a participant. The outcome variable will be coded with a value of "Yes" if the participant had any reported urinary retention over their study duration,

Variable	Туре	Definition
		identified by MEDRA coding preferred term of "Urinary retention". If no urinary retention events were reported for a participant, the outcome variable will be coded with a value of "No".
		Final database lock review took efforts to query sites for participants with reported self- catheterization logs or questionable post void residual results (>200mL, aside from visits immediately post-surgery) and get PI confirmation that all necessary events had been reported.

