		2 □ Rarely 3 □ Sometimes	
		4 □ Usually	
		5 🗆 Always	

Variable	Туре	Definition	
Self-report New/worsening difficulty emptying bladder (UDI item J)	Dichotomous 1=yes 0=no	Self-report of new or worsening difficulty emptying bladder is captured on the UDI for item J at baseline and 6 months (and 3, 9, and 12 months). The outcome variable will coded with a value of "Yes" if any post-baseline UDI assessment reported a worse bo than at baseline (ordered categories are "No", "Yes" with bother not specified / "Not all", "Yes" and "Slightly", "Yes" and "Moderately, "Yes" and "Greatly"). For participants that did not have any post-baseline visits, the outcome variable will be se missing.	
		UDI item J:	
		Do you experience difficulty emptying your bladder?	
		Yes No (Skip to K.)	
		If yes, how much does it bother you?	
Other AEs or symptoms of interest	Dichotomous 1=yes 0=no	 We will also look to see if there are any additional AEs to report on the AE table, covering the following: These will be identified via evaluation of AE preferred terms, verbatim descriptions/comments and AE relationship at least possibly related. Other MUS surgical wound healing problems >6 weeks New/worsening vaginal infection Other infection possibly related to intervention New/worsening partner dyspareunia 	
		At final database lock review, 2 additional event terms of interest were identified: "pyelonephritis", and "Gonococcal pelvic inflammatory disease". Appropriate indicator variables will be created for each additional term of interest, coded to "Yes" if the participant has any reported events coded to the respective MEDRA preferred term. The outcome variable will be set to "No", otherwise.	

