Vaginal mesh exposure (sling only)	Captured by chart review, physician report, exam, or patient report corroborated by medical documentation
Vaginal mesh erosion into organ (sling only)	Captured by chart review, physician report, exam or patient report corroborated by medical documentation
Other wound healing problems >6 weeks (sling only)	Captured by chart review, physician report, exam or patient report corroborated by medical documentation
New/worsening vaginal infection (sling or Botox)	Captured by chart review, physician report, exam, or patient report corroborated by medical documentation
Urinary tract infection beyond 2 weeks (sling or Botox)	UTI based on clinical judgment or confirmation of culture proven, also includes empiric antibiotic treatment for symptoms thought to be due to UTI, or patient report corroborated by medical documentation. If a culture is sent that turns out to be negative, this would not be classified as a UTI. Captured by chart review, physician report, or patient report corroborated by medical documentation
Other infection possibly related to intervention (sling or Botox)	Infection diagnosed using clinical or radiologic indicators – not including vaginal infection, UTI Captured by chart review, physician report, or patient report corroborated by medical documentation
Non-study health care provider visit due to complication related to intervention (sling or Botox)	Captured by chart review, physician report, or patient report corroborated by medical documentation
Emergency room visit due to complication related to intervention (sling or Botox)	Captured by chart review, physician report, or patient report corroborated by medical documentation
Hospital readmission related to intervention (sling or Botox)	Captured by chart review, physician report, or patient report corroborated by medical documentation
Reoperation related to surgery (any return to OR for issue related to intervention (e.g. recurrent SUI, UUI/OAB) (sling only)	Captured by chart review, physician report, or patient report corroborated by medical documentation
An adverse event that is "unexpected" and "possibly, probably or definitely related"	Captured by chart review, physician report, or patient report corroborated by medical documentation

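### No safety variable gives the proportion of women with any urinary tract infection, because SAP 9.2 builds UTI from one preferred term and leaves out pyelonephritis and events marked recurrent

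*SAP*

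**What the plan says.** SAP 3.2.4 lists the proportion of women in each group with UTI and with recurrent UTI among the safety outcomes. The safety aim in Protocol 1.2 calls for the same comparison. SAP 10.1 compares arms by chi-square or Fisher's exact test with descriptive p-values.

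SAP 9.2 derives the variables from the adverse event forms:

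- UTI is Yes for an event "identified by MEDRA coding preferred term of 'Urinary tract infection' and 'recurrent' is NOT specified" in the verbatim term or comments. The default is stated: "If no acute UTI events were reported for a participant, the outcome variable will be coded with a value of 'No".
- Recurrent UTI is Yes for the same preferred term when the word recurrent does appear in the verbatim term or comments.
- Under other adverse events of interest: "At final database lock review, 2 additional event terms of interest were identified: 'pyelonephritis', and 'Gonococcal pelvic inflammatory disease". Each gets its own Yes/No indicator based on its own preferred term.

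SAP 10.2 gives a clinical definition of UTI: clinical judgment, culture confirmation, or empiric antibiotic treatment. It is not tied to a preferred term, and it adds: "If a culture is sent that turns out to be negative, this would not be classified as a UTI". The row for other infections is defined as "not including vaginal infection, UTI". Section 10.2 introduces its table by saying that the variable definitions are in 9.2, so the two sections should describe one outcome.

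**The concern.** The 9.2 rule is narrower than the 10.2 definition in two ways. It recognises one preferred term, and it splits that term into acute and recurrent variables without rejoining them. An infection coded to another urinary tract term falls outside both variables. The SAP's own lock review shows that at least one such term, pyelonephritis, is in the data.

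UTI is a safety outcome on which the two treatments may well differ, and readers will take the UTI row as the share of women who had a urinary infection. As coded, it is the share with at least one event under one preferred term not marked recurrent. A woman with only pyelonephritis, or only recurrent UTI, is counted in that row as having had none.

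**Working it through.** The plan states no UTI rate to reproduce, so the check applies the 9.2 rules to event patterns and then scales the result.

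**Step 1: apply the rules.** The last column is what a person-level indicator would show. It treats pyelonephritis as an infection of the urinary tract. That is general medical knowledge; the documents neither state nor deny it.

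| Events reported for a woman | UTI | Recurrent UTI | Pyelonephritis | Any UTI (not in SAP) |
|---|---|---|---|---|
| Pyelonephritis only | No | No | Yes | Yes |
| Pyelonephritis and a UTI not marked recurrent | Yes | No | Yes | Yes |
| Only UTI events marked recurrent | No | Yes | No | Yes |
| Pyelonephritis and a UTI marked recurrent | No | Yes | Yes | Yes |

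Three of the four patterns are No in the UTI row. The first is No on both UTI variables.

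**Step 2: can the missing proportion be rebuilt from the published lines?** No. If *a*, *r* and *p* women are Yes on the acute, recurrent and pyelonephritis lines, the number with any UTI lies between max(*a*, *r*, *p*) and *a* + *r* + *p*, depending on overlap. For example, assume 24 of 73 on the acute line and 3 women in total on the other two. The number with any UTI is then between 24 (24/73 = 32.9%) and 27 (27/73 = 37.0%). The separate lines cannot say which.

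**Step 3: size per woman.** SAP 6 plans 73 randomized and 69 evaluable per arm. One woman is 1/73 = 1.37 or 1/69 = 1.45 percentage points. The documents give no count of affected women. Assuming 1 to 3 in one arm, the shift is 1/73 = 1.4, 2/73 = 2.7 or 3/73 = 4.1 points. It could also be zero. The true safety denominator is women treated, which may be slightly below 73.

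**Step 4: effect on the comparison (illustration only).** Take 24/73 (32.9%) against 17/73 (23.3%), close to the 33% for Botox A 100 units in ABC and 24% for sling only in ESTEEM (Protocol Table 3). Adding 0, 1, 2 or 3 women to the higher arm gives 32.9, 34.2, 35.6 and 37.0%, with chi-square p-values (no continuity correction) of 0.197, 0.144, 0.102 and 0.071. With 10/73 (13.7%) in the lower arm, p goes from 0.006 to 0.001. Neither case crosses 0.05. These rates are assumptions: Table 3 spans 9 to 24% for sling and 4.8 to 36% for Botox A 100 units, and the plan adopts no expected rate.

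**Step 5: compare 9.2 with 10.2.** Section 10.2 uses a clinical definition, excludes negative cultures, and labels the row as UTI beyond 2 weeks. Section 9.2 uses one preferred term, states no culture rule, and counts events over the whole study. It also notes 8 UTIs between randomization and treatment. The lock queries it describes look for unreported events; they do not address culture results.

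**The case against.** The strongest reply is that nothing is concealed. Pyelonephritis has its own indicator for the adverse event table, and SAP 10.2 summarises all events by system organ class and preferred term, by treatment group and by severity. Serious events are also summarised under SAP 10.3. Showing pyelonephritis beside UTI rather than inside it can be called a presentation choice, and no formal test depends on it. This stands as to visibility and weight. It does not supply the missing proportion, because separate person-level lines cannot be added without knowing the overlap.

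A reader might infer four stronger things that the documents do not support:

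- That every woman with pyelonephritis is coded as having no UTI. If she also has a UTI event not marked recurrent, she is Yes.
- That the most serious infections are missing from the report. They are missing from the UTI row only.
- That cystitis or other kidney infections were also lost. The lock review named only pyelonephritis and one gonococcal term. It considered events at least possibly related, so it does not rule out other terms in the full listing, but none is documented.
- That culture-negative episodes are counted. The 10.2 exclusion can operate when the site classifies the event. The SAP does not say whether it does, and no such case is shown.

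**Conclusion.** The point holds as a gap in a named descriptive safety outcome. Under SAP 9.2, a woman with only pyelonephritis is No for UTI and recurrent UTI, a woman with only events marked recurrent is No for UTI, and no variable reports any urinary tract infection. The size is about 1.4 percentage points per affected woman. The total effect cannot be computed because the number of such women is not given, and it may be small or nil. The conclusion rests on reading the 9.2 rules literally and on treating pyelonephritis as a urinary tract infection. The primary and secondary outcomes are untouched.

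**What to change.** Add to SAP 9.2 a person-level 'any UTI' indicator. It is Yes if the woman has an acute UTI, a recurrent UTI, pyelonephritis, or any other urinary tract infection preferred term present in the adverse event listing. Draw the term list from the pooled listing without reference to arm. Compare this indicator between arms, and keep the acute, recurrent and pyelonephritis lines as sub-rows. A single pyelonephritis should not count as recurrent UTI.

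Reconcile 9.2 with 10.2 by stating that the negative-culture exclusion is applied when the site classifies the event or on review of adverse event text, and by stating the time window. If pyelonephritis is meant to sit outside UTI, say so and why.

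The indicator needs a short term list, a few sentences and no new data. A text check for negative cultures may take some review or site queries, since the SAP 4.6 schedule lists a urine dip but no culture form. The reported UTI rate may rise slightly.

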3.1.2 Exploratory Aims

Exploratory aims of this study (consolidated from the main protocol and the 12-month addendum) are the following:

- 1. **12-month aim:** To compare the effectiveness of intradetrusor injection of 100 units of Botox A to mid-urethral sling for change in MUI symptoms 12 months following treatment
- 2. Secondary urinary outcomes: To compare treatment with Botox A to treatment with mid-urethral sling for improving the number of urinary incontinence episodes on bladder diary 6 and 12 months post-treatment.
- 3. **Predictors of poor treatment response:** To develop models to identify baseline predictors of change of MUI, OAB, and SUI outcomes measured using the UDI, between baseline and 6 and 12 months post-treatment.
- 4. **Quality of life and global impression:** To compare quality of life outcomes and Patient Global Impression-Improvement (PGI-I), Patient Global Impression-Severity (PGI-S) between groups randomized to Botox A versus mid-urethral sling 6 and 12 months post-treatment.
- 5. **Safety and additional treatments:** To describe rates of reoperation (sling revision) after mid-urethral sling and intermittent catheterization due to voiding dysfunction/partial urinary retention after Botox A detrusor injection, to compare the proportion of women in each group with UTI and recurrent UTI, rates of other serious and non-serious adverse events, and to compare the proportion of women in each group initiating additional (off protocol) treatment other than Botox A and mid-urethral sling for SUI and/or OAB.
- 6. **Cost-effectiveness analysis:** To determine the cost effectiveness of Botox A injection versus mid-urethral sling for the treatment of MUI symptoms on an intent-to-treat basis 6 and 12 months post-treatment.
- 7. **UDI MID:** To explore MIDs for UDI total score and stress and irritative subscores for this MUI population.

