3.2.4 Safety Outcomes

[figure not shown]
- Rates of reoperation or sling revision due to worsening OAB after MUS
- Rates of urinary retention / intermittent catheterization after Botox injection,
- Proportion of women in each group with UTI and recurrent UTI,
- Rates of other serious and non-serious adverse events,

Safety outcomes will be assessed in a descriptive manner at each DSMB meeting without formal statistical tests. There is no established stopping rule to guide what sling revision rate is "appropriate" for worsening OAB symptoms in this population.

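### SAP 9.2 sorts UTI events into acute and recurrent by one word on the adverse event form, so the UTI proportion is not any UTI and the recurrent UTI proportion depends on form wording

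*SAP*

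**What the plan says.** Protocol 1.2 and SAP 3.1.2 both set the aim "to compare the proportion of women in each group with UTI and recurrent UTI". SAP 3.2.4 lists the same pair as a safety outcome.

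SAP 9.2 gives the derivation, working from all adverse event forms over a woman's time on study:

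- The variable labelled UTI is Yes if any form has "MEDRA coding preferred term of 'Urinary tract infection' and 'recurrent' is NOT specified by verbatim adverse event term or comments". Otherwise: "If no acute UTI events were reported for a participant, the outcome variable will be coded with a value of 'No".
- The variable labelled recurrent UTI is Yes if any form has "MEDRA coding preferred term of 'Urinary tract infection' and 'recurrent' is specified by verbatim adverse event term or comments". Otherwise: "If no recurrent UTI events were reported for a participant, the outcome variable will be coded with a value of 'No".

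For both variables, the review at database lock was to "query sites for participants with questionable urine test results and get PI confirmation that all necessary events had been reported".

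SAP 10.2 describes what counts as a UTI beyond 2 weeks and refers back to 9.2 for variable definitions. It also plans a general table of adverse events by preferred term, giving numbers of events and of women per arm.

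**The concern.** Recurrence is a matter of how many infections a woman has over a period. The adverse event log holds separate events with onset dates, but the rule uses neither the count nor the dates. It sorts events with the same preferred term into two exclusive classes according to whether one word was written on the form.

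Two named between-arm outcomes are affected. The recurrent UTI proportion reflects recording habit as well as infection. The UTI proportion will be read as any UTI, because the aim, the safety outcome and the row label all say UTI, yet it leaves out women whose only form uses the word *recurrent*. UTI matters to the comparison of these treatments: Protocol Table 3 tabulates its rates for both, and Protocol 7.5.4 singles out multiple recurrent UTIs during treatment as a benefit-risk consideration for Botox A.

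**Working it through.** The plan states no figure for these variables, so there is none to reproduce. The check applies the rule literally and then asks how much could be at stake.

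**1. The rule on test cases.** Each form carries the preferred term for urinary tract infection. UTI = Yes if at least one form lacks *recurrent*; recurrent UTI = Yes if at least one form has it.

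| Forms for one woman | UTI | Recurrent UTI |
|---|---|---|
| Four forms reading *UTI*, word absent | Yes | No |
| One form reading *recurrent UTI* | No | Yes |
| Two forms reading *UTI*, one reading *recurrent UTI* | Yes | Yes |
| One form reading *UTI*, comment *no recurrent symptoms* | No | Yes |

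Row 1 misses recurrence and row 2 drops a woman from the UTI proportion. Row 4 is a false Yes on recurrence. It arises if the rule is run as a plain text match; the SAP does not say whether a person reads the comments.

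**2. Does another section repair it?** The protocol names recurrent UTI in 1.2, 3.4.3.c, 6.2.3 and the addendum without defining it. SAP 10.2 has no recurrence rule. The lock review for UTI asked whether events had been reported, not whether they were classed correctly. Neighbouring rows of SAP 9.2 go further: query answers were used to separate urinary retention from residual urine volume, and investigators confirmed self-catheterization in the comments field. No such check is described for *recurrent*.

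**3. Possible effect on the UTI proportion.** Inputs from Protocol Table 3: 33% (ABC trial, Botox A 100 units) and 24% (ESTEEM, sling only), a difference of 9.0 points. Assumption: a share *s* of women with any UTI is logged only as recurrent. Then

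reported proportion = true proportion × (1 − *s*).

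| *s* sling | *s* Botox A | Sling | Botox A | Difference (points) |
|---|---|---|---|---|
| 0 | 0 | 24.0% | 33.0% | 9.0 |
| 10% | 10% | 21.6% | 29.7% | 8.1 |
| 20% | 20% | 19.2% | 26.4% | 7.2 |
| 0 | 20% | 24.0% | 26.4% | 2.4 |
| 0 | 30% | 24.0% | 23.1% | −0.9 |

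The documents give no value for *s*.

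**4. How many women could have repeat infections.** If infections follow a Poisson process and *p* is the proportion with at least one, the mean is λ = −ln(1 − *p*) and P(two or more) = *p* − λ(1 − *p*).

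- *p* = 0.33: λ = 0.400, P = 0.062, and 0.062 × 73 = 4.5 women.
- *p* = 0.24: λ = 0.274, P = 0.031, and 0.031 × 73 = 2.3 women.

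Table 3 gives 100-unit rates from 4.8% to 36%. At 4.8%, λ = 0.049 and P = 0.001 (0.1 of 73); at 36%, λ = 0.446 and P = 0.074 (5.4 of 73). These figures show only that the count per arm is likely to be small, so the wording of two or three forms could change the comparison. They do not measure the error that the rule makes.

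**The case against.** Much of the case on the other side stands.

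- The definition text calls the first variable acute UTI. Read that way, the two variables are exclusive by design, and a woman logged only as recurrent still counts in the second. A reader might infer that she drops out of the safety data; she does not. What remains is that the label and the aim say UTI while the rule measures something narrower.
- The preferred-term table in SAP 10.2 has no text filter, so any UTI by arm will be visible. It does not correct the two named outcomes, and arm totals do not show how many women had repeat infections.
- A reader might infer that recurrent UTI is undercounted, or that a Botox A excess is hidden. The documents do not support a direction. The rule can give false Yes values as well as false No values, and closer watching for recurrence in one arm could push the comparison either way.
- A reader might also blame unmasked sites. SAP 4.5.1 says surgeons are unmasked and outcome assessors masked; neither document says who words the adverse event forms.
- Relying on a clinician's label is partly defensible, since SAP 10.2 lets UTI itself rest on clinical judgment. That would need a shared definition of recurrent, and none is given.
- The rates in the illustration come from trials that differ in follow-up, and Table 3 describes no UTI definition for the ABC trial.

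**Conclusion.** The point holds on the text. The rule gives a wrong value for recurrent UTI when a woman's repeat infections are logged without the word, and it makes the variable labelled UTI something other than any UTI. Both are pre-specified between-arm safety outcomes, so this goes beyond missing detail.

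The size is unknown. It could be nil if forms were labelled consistently. The illustrated movement, from 9.0 points to between 8.1 and −0.9, rests on assumed shares of women and on rates borrowed from other trials. Neither the direction of the error nor any imbalance between arms is established.

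The p-values for these outcomes are descriptive (SAP 7.8 and 10.1), and the primary and secondary efficacy analyses are untouched. The change is worth making because it is cheap and the outcomes will be quoted.

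**What to change.** - Code UTI = Yes for any adverse event with the urinary tract infection preferred term, whether or not *recurrent* appears.
- Derive recurrent UTI from the number and onset dates of separate UTI events per woman. Use one count-and-window threshold chosen by the sponsor, stated before unmasking and applied equally to both arms. The documents offer no threshold, and none is proposed here.
- Use the keyword only to trigger a query for the number and dates of episodes behind a single *recurrent UTI* form. State the default if these cannot be obtained: count the woman as recurrent.
- State how incomplete onset dates are handled, which SAP 10.2 already anticipates. State also whether infections between randomization and treatment count, since SAP 9.2 reports eight of them.
- If the data are already unmasked, report the re-derived outcomes beside those from the existing rule, labelled as such.

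The cost is two revised definitions in SAP 9.2 and minor recoding. Some site queries may be needed where one form covers several episodes.
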